7.2 PARTICIPANT DISCONTINUATION/WITHDRAWAL FROM THE STUDY

If a participant does withdraw, or is lost to follow up, the Study Termination Case Report Form (CRF) will be completed and entered into REDCapTM. The study team will document the reason for participant discontinuation and log the information into an excel file noting that participation is no longer active. Reasons for mothers to be withdrawn from the study or be lost to follow-up may include, but is not limited to mother and/or child moving out of the state, mother losing the child's custody, mother opting to withdraw from study due to having a child born with medical and/or special health care needs conditions that require specialized care and/or hospitalization preventing participation in study activities, etc.

7.3 LOST TO FOLLOW-UP

A study WIC mother will be considered lost to follow-up if she is unable to be contacted by the study team to schedule and participate in their WIC site visit activities at year 2, 3 or 4. If participants miss WIC site visits 2 and/or 3, they can still return to the consecutive WIC site visit(s) but will not complete the post-intervention activities (1- and 9-month follow-ups and 3-month booster message) related to missed WIC site visit(s). The study will not replace lost or withdrawn participants.

The following actions must be taken if a participant fails to return to any of the WIC site visits:

• The study team will attempt to contact the participant, reschedule the missed visit within two months, counsel the participant on the importance of maintaining the assigned visit

schedule and ascertain if the participant wishes to and/or should continue in the study; and

• Before a participant is deemed lost to follow-up, the investigator or designee will make every effort to regain contact with the participant (where possible, three text messages, emails and telephone calls and, if necessary, a letter to the participant's last known mailing address). These contact attempts will be documented in the participant's study file.

Should the participant continue to be unreachable, she will be considered to have withdrawn from the study with a primary reason of lost to follow-up.

8 STUDY ASSESSMENTS AND PROCEDURES

8.1 ENDPOINT AND OTHER NON-SAFETY ASSESSMENTS

Endpoints

The primary outcome of interest is caries status, which will be measured by the d₁d₂₋₃mfscaries criteria for scoring dental caries for the children^{44,45-49} Both d₁mfs and d₂₋₃mfs scores derived from these criteria will be considered, reflecting numbers of affected (cavitated, missing due to caries or filled) surfaces with and without inclusion of non-cavitated (d₁ "white spot") lesions. These caries outcomes will be assessed by dental examinations at 12, 24 and 36 months of age. Secondary outcomes of interest will assess changes in maternal knowledge and oral health behaviors through questionnaires via REDCapTM, as well as children's plaque and microbial outcomes through dental exams and plaque collection done by dental providers who will be blinded to study allocation.

Screening and Enrollment

• The PI and CTRA are responsible for tracking the screening, enrollment, and the number approached, refusals and reasons for refusal. The UI Institute for Clinical and Translational Science IT specialist along with the Database Manager will provide combined enrollment reports of all the WIC sites to the study team and NIDCR.

Visit Procedure Completion

• The study CTRA and RAs are responsible for collecting the data at the WIC sites during visits 1, 2, 3 and 4. Participants will view videos and complete questionnaires on tablets/i-pads through REDCapTM. UI dental providers will conduct dental exams and collect plaque samples for all participating children. The REDCapTM system will ensure that once a study participant is randomly assigned to one of the two study groups, based on the participant language preference (English vs. Spanish), the participant will be linked to her assigned group and study activities in all time points throughout the duration of the study. In addition, the REDCapTM will also allow us to do complex and robust multivariate data checks, which will be critical for flagging the study team for potential issues within the data or potential process issues at the study sites. The Database Manager will provide reports of number of visits completed for each WIC sites.

Retention and Attrition

• The study PI and CTRA are responsible for tracking the recruitment, retention and attrition status throughout the study. Efforts will be made to assess reasons for dropouts.

Data Entry Errors

• The Database Manager is primarily responsible for identifying data entry errors in all WIC Sites. REDCapTM will notify the user during data entry of missing fields flagged as

required by data management, and manual queries may be created and issued by the Data Manager.

Protocol Deviations/Violations

- A protocol deviation is any noncompliance with the clinical study protocol or GCP. The noncompliance may be on the part of the subject, the investigator, or study staff. The study team will review protocol deviations on an ongoing basis and will implement corrective actions when the quantity or nature of deviations are deemed to be at a level of concern. All protocol deviations and violations must be submitted to the UI IRB per its guidelines.
- The CTRA and RAs will be responsible for tracking any deviations/violations. The Protocol Deviations/Violations Tracking Log will be completed and submitted with the report to the Data and Safety Monitoring Board (DSMB). Protocol violations or deviations that meet the definition of an Unanticipated Problem (UP) will be submitted to NIDCR and the Clinical Research Operations and Management Support (CROMS) contractor ([contact]).

8.2 SAFETY ASSESSMENTS

Safety monitoring for this study will focus on parameters that capture risks related to study participation. Therefore, the study will collect adverse events (including serious adverse events) and unanticipated problems (UPs) (Title 45 of the Code of Federal Regulations [CFR] Part 46) All UPs, AEs, and SAEs (as defined below) will be reported, from the time of signed informed consent to participant study completion or termination.

8.3 ADVERSE EVENTS AND SERIOUS ADVERSE EVENTS

8.3.1 DEFINITION OF ADVERSE EVENTS

An adverse event (AE) is any untoward or unfavorable medical occurrence in a human participant, including any abnormal sign (for example, abnormal physical exam or laboratory finding), symptom, or disease, temporally associated with participation in the research, whether or not considered related to participation in the research.

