6.5.1 RESCUE PROCEDURES

Mothers of children diagnosed with caries during the dental exam will be given a list of local dentists to further address their restorative needs. In the course of the children's clinical exams, unexpected conditions might be identified (e.g., dental caries, acute infection, etc.). Should this occur, mothers will be given the following options: 1) to have their children evaluated on the same day on an emergency basis at the UI Department of Pediatric Dentistry, 2) to follow up with their respective local dental providers, or 3) to follow up with the UI Department of Pediatric Dentistry; appointments will be made within 1-4 weeks for further assessment and appropriate treatment. The clinical situation will dictate the urgency of the follow-up care. For example, participants with acute abscess will be strongly encouraged to receive immediate evaluation (e.g., urgent care clinic at UI Department of Pediatric Dentistry or same day visit with their local dentists). Participants with a condition that does not require immediate attention (i.e., asymptomatic dental caries, etc.) could have a longer wait period (e.g. follow up in 4 weeks). In the event that participants decide to follow up with their local dentists, they will be offered the option of a typed document detailing any concerns and oral exam findings. Otherwise, all information collected by the study will be de-identified and not shared with any outside sources.

7 STUDY INTERVENTION/EXPERIMENTAL MANIPULATION DISCONTINUATION AND PARTICIPANT DISCONTINUATION/WITHDRAWAL

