8.3.3.2 RELATIONSHIP TO STUDY INTERVENTION/EXPERIMENTAL MANIPULATION

All AEs will have their relationship to study procedures, including the intervention, assessed by an appropriately-trained clinician based on temporal relationship and his/her clinical judgment. The degree of certainty about causality will be graded using the categories below.

- **Related** The AE is known to occur with the study procedures, there is a reasonable possibility that the study procedures caused the AE, or there is a temporal relationship between the study procedures and the event. Reasonable possibility means that there is evidence to suggest a causal relationship between the study procedures and the AE.
- Not Related There is not a reasonable possibility that the study procedures caused the event, there is no temporal relationship between the study procedures and event onset, or an alternate etiology has been established.

All AEs and SAEs related to this study will be assessed to determine if a protocol amendment will be needed to prevent future occurrences. Corrective and preventive actions will be initiated and the Program Officer at the NIDCR will be notified of these corrective efforts.

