8.3.3.3 EXPECTEDNESS

Expectedness of each event will also be assessed to determine whether it is unexpected (e.g., nature not consistent with the intervention in the protocol, consent form, or other related materials) or expected (event is known to be associated with the provided intervention of this study).

8.3.4 TIME PERIOD AND FREQUENCY FOR EVENT ASSESSMENT AND FOLLOW-UP Any findings which consist of Adverse Events (AE), Serious Adverse Events (SAE) or Unexpected Problems (UP) will be documented on the appropriate Case Report Forms. All AEs, SAEs, UPs, regardless of severity, will be recorded. Potential untoward or unfavorable medical/dental occurrences that occur in a study participant, including any abnormal sign, symptom, or disease (including but not limited to dental pain, dental infection, trauma or other conditions that require immediate attention) that is temporally associated with the subject's participation in the research study (whether or not considered related to the subject's participation in the research) will be identified by all research team members at completion of each study visit and promptly reported to the PI. The PI will record the report on an adverse occurrence report sheet. The PI will also review all reports to determine whether the event is:

- 1) unexpected;
- 2) related or potentially related to research study participation; and/or
- 3) suggests that the research places subjects or others at a greater risk of harm related to the research than was previously known or recognized.

If these three conditions exist, the occurrence will be considered an UP and will be reported to the IRB on the appropriate form and to the NIDCR per their required timeframes. Unanticipated problems will be reported to the DSMB as part of the DSMB reports.

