9.4.6 PLANNED INTERIM ANALYSES

Planned interim analysis

No interim analyses are planned.

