10.1.6 SAFETY OVERSIGHT

The PI will be responsible for study oversight, including monitoring safety, ensuring that the study is conducted according to the protocol and ensuring data integrity. The interventions, outcome measures, and other assessments are of minimal risk to participants in the proposed study. Intervention participation and data assessments do not exceed the probability and magnitude of harm or discomfort anticipated during ordinarily encountered daily life or in the performance of routine oral or psychological examinations or tests. The PI will oversee

recruitment and consenting processes approved for participants and conduct the study using protocols that will be approved by the UI IRB. Systems will be in place to assure confidentiality and data security for data collection and storage. The PI and the CTRA will review the data for safety concerns and data trends at regular intervals and will promptly report to the IRB and NIDCR per their reporting requirements.

In addition to the PI's responsibility for oversight, study oversight will be under the direction of a Data and Safety Monitoring Board (DSMB) composed of members with expertise in obstetrics/gynecology, motivational interviewing and health disparities, pediatric dentistry, and biostatistics. Reports will be provided to the DSMB, including missing data, protocol deviations and safety data, screen fail, enrollment and withdrawal rates, etc. If safety concerns arise, more frequent meetings may be held. The DSMB will operate under the rules of an NIDCR-approved charter that will be approved at the organizational meeting of the DSMB. At this time, most data elements that the DSMB needs to assess will be clearly defined. The DSMB will provide recommendations to the NIDCR.

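### The protocol's adverse event definition takes in the primary endpoint, and its Related and Not Related categories overlap, so one caries finding can be coded either way

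*Protocol*

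**What the plan says.** Section 8.3.1 of the protocol defines an adverse event (AE) broadly, "including any abnormal sign (for example, abnormal physical exam or laboratory finding), symptom, or disease", provided it is temporally associated with taking part, whether or not it is thought to be related. Section 8.3.4 sets no severity threshold: "All AEs, SAEs, UPs, regardless of severity, will be recorded". Its dental examples form an open list: "including but not limited to dental pain, dental infection, trauma or other conditions that require immediate attention". Caries is neither named there nor excluded.

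Caries status at the 12, 24 and 36 month exams is the primary outcome (8.1). Section 6.5.1 (rescue procedures) says that at those exams "unexpected conditions might be identified (e.g., dental caries, acute infection, etc"; it gives referral options but does not say whether such a finding is an AE.

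Section 8.3.3.2 has a trained clinician grade causality. One of the three alternatives that make an event Related is "or there is a temporal relationship between the study procedures and the event". One of the three that make it Not Related is "or an alternate etiology has been established". Events related to the study are then assessed for a protocol amendment, corrective and preventive actions follow, and the Program Officer is notified. Section 8.3.5 sends AEs deemed expected and/or unrelated into an annual summary.

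**The concern.** Two stated rules do not work as written. The AE definition has no boundary between the disease the trial is measuring and harm that its procedures might cause. The causality grading has two categories that are not mutually exclusive, so two clinicians could grade the same event in opposite ways and both comply.

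What is at stake is the usefulness of the safety record. Section 8.2 says that safety monitoring focuses on risks related to study participation, and section 2.3.1 describes those risks as minimal. If a common endpoint is logged in the same channel, the few events that an exam or a swab might really cause are diluted, and the relatedness code says little about them. AE definitions and causality categories belong in the protocol, so a separate analysis plan would not normally repair this.

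**Working it through.** The point rests on definitions, so the check is mainly a side-by-side reading. The arithmetic only shows scale.

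**Step 1. Is exam-detected caries an AE?**
- 8.3.1 requires an unfavourable medical occurrence, and an abnormal exam finding or a disease counts. Caries is both.
- 8.3.1 requires temporal association with participation. A finding at a scheduled study exam after consent meets this on a plain reading.
- 8.3.4 requires recording at any severity.
- Exemption: none in 8.1, 8.2, 8.3.1 or 8.3.4. Section 8.3.8 (events of special interest) is marked not applicable, so there is no separate handling there either.

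Result: recordable on the literal text.

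**Step 2. How is it graded under 8.3.3.2?**

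| Category | Alternatives, joined by 'or' | Can caries found at an exam meet it? |
|---|---|---|
| Related | known to occur with the procedures; reasonable possibility of causation; temporal relationship | Arguably yes, by the third alone |
| Not Related | no reasonable possibility of causation; no temporal relationship to onset; other cause established | Yes, by the first or the third (2.2 attributes caries mainly to sugar intake, oral hygiene and early bacterial colonisation) |

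Result: both categories are open to the same event. Because 8.3.1 already builds temporal association into the definition of an AE, the timing alternative separates almost nothing.

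**Step 3. Does the code have consequences?**
- Related: amendment assessment, corrective and preventive actions, and notice to the Program Officer (8.3.3.2).
- Not Related: annual summary (8.3.5). An event deemed expected also takes this route, so the code decides the route for events not deemed expected.
- Related is also one of the three conditions for an unanticipated problem in 8.3.4; the other two must be met as well.

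Result: two compliant codings of one finding lead to different handling.

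**Step 4. Scale, for illustration only.**
- Expected completers (9.2): 317 per group with 21% annual attrition gives 317 × 0.79³ = 156.3, which reproduces the stated 156 per group; 2 × 156 = 312.
- Caries rates cited in 2.2 for WIC-enrolled children under three: 35% to 56%.
- 312 × 0.35 = 109.2 and 312 × 0.56 = 174.7, so about 109 to 175 children with at least one such finding. Repeat findings over the three exams are not counted.

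**The case against.** **Narrower capture may be intended.** Section 8.2 directs safety monitoring to risks of participation. The dental examples in 8.3.4 lean towards conditions needing prompt attention, while 6.5.1 describes asymptomatic caries as not needing it. This is a fair reading of intent, but the list is explicitly open and the definition in 8.3.1 is not limited by it.

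**Clinician judgment.** A reader might infer that every caries finding must be coded Related because of timing. The text does not fix that. Caries fits Not Related at least as well, the assessor uses clinical judgment, and detecting an existing lesion at an exam does not make its onset temporally related to that exam. This objection stands against the strong reading. It does not cure the overlap, because judgment is being exercised between two categories that can both apply.

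**Expectedness.** A reader might take the word in 6.5.1 as a formal classification. It is ordinary prose about referral; expectedness is defined separately in 8.3.3.3. It therefore does not follow that each caries finding is both related and unexpected.

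**Blinding and interim looks.** A reader might infer an unplanned look at the endpoint: section 10.1.6 says "The PI and the CTRA will review the data for safety concerns and data trends at regular intervals", the clinical trial research associate (CTRA) is unblinded (6.3), and 9.4.6 says "No interim analyses are planned". The documents do not support that step. No section tabulates AEs by arm, and a pooled safety listing is not an interim analysis. The CTRA and research assistants already collect visit data (8.1), and the CTRA checks data accuracy (6.2.1), so AE recording gives them no evident new access. The examiners who score caries are blinded.

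**Limited consequence.** Section 9.4.4 marks safety analyses as not applicable, so relatedness feeds no planned analysis. That stands and keeps the severity low.

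**Conclusion.** Wrong as written, low severity. Two points hold on the text: caries scored as the primary endpoint is a recordable AE because nothing exempts it, and the Related and Not Related definitions overlap, so one event can be coded either way with different follow-on handling.

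The figure of 109 to 175 children assumes that the literature range in 2.2 applies to this sample, that 312 children complete, and that every caries finding is logged as an AE. It indicates order of magnitude only. Dilution of genuine procedure-related events is a plausible consequence, not a demonstrated one. No effect on the primary estimate and no comparative look at the endpoint is shown.

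**What to change.** - **8.3.1:** state that caries, white-spot lesions, plaque and mutans streptococci scored at study exams are study endpoints and are not reported as AEs, while complications such as pain or infection still are.
- **6.5.1:** reconcile the reference to caries as an unexpected condition with that statement. The referral steps are not affected.
- **8.3.3.2:** make the two categories mutually exclusive, so that Related requires a reasonable possibility that study procedures caused the event and timing alone does not suffice; everything else is Not Related.

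The cost is amendment wording in two sections plus a one-line alignment in 6.5.1. It needs no new data, leaves sample size and analysis unchanged, and should reduce reporting work.

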8.3.2 DEFINITION OF SERIOUS ADVERSE EVENTS

SAE is one that meets one or more of the following criteria:

- Results in death
- Is life-threatening (places the participant at immediate risk of death from the event as it occurred)
- Results in inpatient hospitalization or prolongation of existing hospitalization
- Results in a persistent or significant disability or incapacity
- Results in a congenital anomaly or birth defect
- An important medical event that may not result in death, be life threatening, or require hospitalization may be considered an SAE when, based upon appropriate medical judgment, the event may jeopardize the study participant and may require medical or surgical intervention to prevent one of the outcomes listed in this definition.

8.3.3 CLASSIFICATION OF AN ADVERSE EVENT

8.3.3.1 SEVERITY OF EVENT

Each of the AEs and SAEs will be assessed based on the classification systems considering three factors: severity and expectedness of the event and relatedness to this study. Severity of the event will be determined using the classifications outlined below:

- Mild (e.g., signs or symptoms easily tolerated, are of minor irritant not causing loss of time from normal activities or oral function, and do not require therapy or medical/dental evaluation).
- **Moderate** (e.g., a low level of inconvenience or concern, may interfere with daily activities or functioning, improved by simple measures);
- Severe (e.g., interrupt normal daily activities, require systemic drug therapy or treatment, incapacitating in performing oral function).

8.3.3.2 RELATIONSHIP TO STUDY INTERVENTION/EXPERIMENTAL MANIPULATION

All AEs will have their relationship to study procedures, including the intervention, assessed by an appropriately-trained clinician based on temporal relationship and his/her clinical judgment. The degree of certainty about causality will be graded using the categories below.

- **Related** The AE is known to occur with the study procedures, there is a reasonable possibility that the study procedures caused the AE, or there is a temporal relationship between the study procedures and the event. Reasonable possibility means that there is evidence to suggest a causal relationship between the study procedures and the AE.
- Not Related There is not a reasonable possibility that the study procedures caused the event, there is no temporal relationship between the study procedures and event onset, or an alternate etiology has been established.

All AEs and SAEs related to this study will be assessed to determine if a protocol amendment will be needed to prevent future occurrences. Corrective and preventive actions will be initiated and the Program Officer at the NIDCR will be notified of these corrective efforts.

